4 DETERMINATION OF SAMPLE SIZE

A total of up to 45 subjects will be enrolled. In each of the histology groups of RMS, NRSTS, and EWS, approximately 15 subjects will be enrolled and treated with eribulin mesylate. The

sample size is considered sufficient based on clinical judgment and is not obtained from statistical calculation.

5 STATISTICAL METHODS

All descriptive statistics for continuous variables will be reported using n, mean, standard deviation, median, 25th percentile (Q1), 75th percentile (Q3), minimum, and maximum. Categorical variables will be summarized as number and percentage of subjects.

All summary tables will be presented by histology type and overall.

5.1 Study Endpoints

5.1.1 Primary Endpoint

- Objective response: number of subjects achieving a best overall response of partial or complete response (PR or CR), by up to 24 weeks after all subjects have completed response assessment. Response assessment will be determined by investigators.

5.1.2 Secondary Endpoints

- PFS: defined as the time from the first dose date to the date of disease progression or date of death (whichever occurs first).
- Safety and tolerability: AEs, SAEs, clinical laboratory values, ECG parameters, vital sign measurements, and performance status.
- DOR: defined as the time from the first date of documented PR or CR to the date of disease progression or date of death (whichever occurs first).
- OS: defined as the time from the first dose date to the date of death.

5.1.3 Exploratory Endpoint

- Exposure of eribulin mesylate.

5.2 Study Subjects

5.2.1 Definitions of Analysis Sets

The **Full Analysis Set** (FAS) will consist of all subjects who receive at least 1 dose of study drug.

The **Safety Analysis Set** will consist of all subjects who receive at least 1 dose of study drug.

The **Pharmacokinetic Analysis Set** (PAS) will include subjects who have at least 1 evaluable plasma concentration and sufficient dosing information.

5.2.2 Subject Disposition

Screening disposition will be summarized by number and percentage of subjects with reasons.

Study treatment disposition will be summarized by number and percentage of subjects with reasons for treatment discontinuation.

5.2.3 Protocol Deviations

Protocol deviations will be determined prior to database lock. The protocol deviations data as collected in the clinical database will be presented in tables and/or listings as appropriate.

5.2.4 Demographic and Other Baseline Characteristics

Demographic and other baseline characteristics for the Full Analysis Set will be summarized for each histology group and overall using descriptive statistics. Continuous demographic and baseline variables include age (years), height (cm), weight (kg), BSA (m²), and vital signs, categorical variables include country, sex, age group, ethnicity, race, Karnofsky (for age>16) / Lansky (for age<=16) performance status score.

For continuous variables, the number of non-missing observations, mean, standard deviation, median, 25th percentile (Q1), 75th percentile (Q3), minimum, and maximum will be presented. For categorical variables, the number and percentage of patients will be presented.

5.2.4.1 Medical History

Medical history will be coded by MedDRA (Version 21.1 or higher), the linked MedDRA preferred term (PT) and primary system organ class (SOC) will also be captured in the database. The number (percentage) of subjects in the Full Analysis Set reporting a history of any medical condition, will be summarized by SOC and PT for each histology group and overall. A subject data listing of medical history will be provided.

5.2.4.2 Disease History and Characteristics

Disease history and characteristics for the Full Analysis Set will be summarized for each histology group and overall using descriptive statistics.

Continuous variables include:

- Time from first diagnosis to first dose (months);
- Age at first diagnosis (years);
- Time from last disease progression to first dose (days);

Categorical variables include:

- Location of primary tumor;

- Target lesions at baseline (Lymph node only, Non-lymph node only, Lymph node and non-lymph node);
- Non-target lesions at baseline (Yes and No);

A subject data listing of disease history and characteristics will be provided.

5.2.5 Prior and Concomitant Therapy

All investigator terms for medications recorded in the CRF will be coded to an 11-digit code using the World Health Organization Drug Dictionary (WHODDMAR18_HD_B2). The number (percentage) of subjects who took prior and concomitant medications will be summarized on the Full Analysis Set by histology group, Anatomical Therapeutic Chemical (ATC) class (i.e., anatomical class, pharmacologic class), and WHODD preferred term.

Prior medications are defined as medications that stopped before the first dose of study drug. Concomitant medications are defined as medications that (1) started before the first dose of study drug and were continuing at the time of the first dose of study drug, or (2) started on or after the date of the first dose of study drug up to 28 days after the subject's last dose. A medication that cannot be determined as prior/concomitant/post-treatment due to missing/incomplete dates will be regarded as a concomitant medication.

Prior and concomitant medications will be summarized respectively. All medications will be presented in subject data listings.

Previous anticancer therapies

Number of regimens, type of regimens, duration of last regimen (months), time from end of last regimen to first dose (months) and best response to the last regimen will be summarized for prior anticancer medications.

The number (percentage) of subjects who took prior anticancer medications will be summarized on the Full Analysis Set by histology group, Anatomical Therapeutic Chemical (ATC) class (i.e., anatomical class, pharmacologic class), and WHODD preferred term.

Number of radiotherapy, sites of radiotherapy, total dose (cGy) per subject, time from end of last radiotherapy to first dose (months) and tumor lesion progressed since most recent radiotherapy, will be summarized for prior anticancer radiotherapy.

Previous anticancer medication and radiotherapy will be summarized/listed separately.

5.2.6 Treatment Compliance

Not applicable.

5.3 Data Analysis General Considerations

5.3.1 Pooling of Centers

This study is a multicenter study. Subjects from all centers will be pooled for all analyses.

5.3.2 Adjustments for Covariates

Not applicable.

5.3.3 Multiple Comparisons/Multiplicity

Not applicable.

5.3.4 Examination of Subgroups

No subgroup analyses are planned for this study.

5.3.5 Handling of Missing Data, Dropouts, and Outliers

In general, missing data including dates will be treated as missing and no data imputation will be applied, unless otherwise specified. Data that are potentially spurious or erroneous will be queried and examined during the review of the study data.

For efficacy data summarized for the FAS, subjects with missing response status (subjects whose baseline or post-baseline tumor assessment is missing) will be considered as non-responders and will be included in the denominator when calculating the response rate.

5.3.6 Other Considerations

Not applicable.

5.4 Efficacy Analyses

Efficacy analyses will be performed on the Full Analysis Set.

5.4.1 Primary Efficacy Analyses

The primary analysis will be based on investigator assessments of tumor response according to RECIST 1.1 ([Eisenhauer, et al. 2009](#)).

The primary analysis is to examine the number of responders (CR or PR) within each histology subject cohort. Confirmed response (PR or CR) will be used in this analysis. All responses must be confirmed no less than 28 days following the initial assessment of response. In order for stable disease (SD) to be considered the best overall response, it must occur ≥ 5 weeks following the first dose of study drug.

Objective response rate (ORR) is defined as the proportion of subjects achieving the best overall response (BOR) of CR or PR as per RECIST 1.1. ORR will be calculated with a 2-sided, exact 95% confidence interval (CI), using the Clopper-Pearson method.

5.4.2 Secondary Efficacy Analyses

The secondary analyses will be to estimate the PFS, DOR, and OS in all cohorts combined. Median PFS, DOR, and OS with the corresponding 95% confidence intervals (CI) will be estimated using Kaplan-Meier method (Kaplan; Meier. 1958). Descriptive statistics will be provided. Duration of response (DOR) will be calculated for subjects with an objective response of PR or CR.

Censoring rules for PFS/DOR are listed in [section 8](#): definitions and conventions for data handling. For OS, subjects who were alive at the data cutoff date will be censored at the data cutoff date, and subjects who were lost to follow-up, withdrew consent, or had survival status collected as “Study terminated by Sponsor” will be censored at the date the subject was last known to be alive.

5.4.3 Other Efficacy Analyses

No other efficacy analyses are planned for this study.

5.5 Pharmacokinetic, Pharmacodynamic, Pharmacogenomic, and Other Biomarker Analyses

5.5.1 Pharmacokinetic Analyses

Blood samples will be collected for the PK analysis of eribulin as follows:

1. Immediately post-infusion on Day 1 of each cycle for the first 3 cycles;
2. Pre-infusion and immediately post-infusion on Day 8 of each cycle for the first 3 cycles.

Plasma concentrations of eribulin will be tabulated and summarized by histology and time.

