The primary analysis is to examine the number of responders within each histology subject cohort. Confirmed response (PR or CR) will be used in this analysis. In each of the histology groups of RMS, NRSTS, and EWS, approximately 15 subjects will be enrolled and treated with eribulin mesylate. Data will be monitored on an ongoing basis; depending on evaluation by the investigators and sponsor, if sufficient responses (partial response [PR] or complete response [CR]) are observed,

then this histology type will be recommended for inclusion in the subsequent study. At the latest, the primary analysis will be performed when approximately 15 subjects have completed 24 weeks of response assessments.

Secondary Efficacy Analyses

The secondary analyses will be to estimate the PFS, DOR, and OS in all cohorts combined. Median PFS, DOR, and OS will be estimated using Kaplan-Meier method.

Pharmacokinetic Analyses

Observed eribulin concentrations from this study will be overlaid with existing observed concentrations and model-predicted 90% prediction intervals at the same dose level from other studies to demonstrate comparability in exposure.

Safety Analyses

Safety analyses will be performed on all subjects who receive at least 1 dose of study drug. It will include safety data collected from screening to data cut-off. Safety data include the incidence and severity of AEs, clinical laboratory test results, performance status, ECG readings, and vital signs measurements.

Vital signs, resting 12-lead ECGs, hematology, clinical chemistry, and urinalysis data will be listed. Descriptive summary statistics (mean, standard deviation, median, minimum, and maximum) of clinical laboratory test results, vital signs measurements, ECG parameters, and changes from Baseline will be presented by cohort and overall. Treatment-emergent abnormal laboratory test results, vital signs, and ECGs will be listed.

All AEs and SAEs will be listed. Treatment-emergent AEs (TEAEs), treatment-related TEAEs, and SAEs will be summarized by cohort, system organ class, preferred term, and CTCAE v. 4.03 grade. QT intervals will be measured from Lead II and will be corrected for heart rate (QTc) using QTcF and QTcB correction factors. The primary QTc parameter will be QTcF. Secondary parameters will be QTcB, QT, QRS, and heart rate.

Interim Analyses

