9.4.1.1.1 ERIBULIN MESYLATE

Treatment will not be administered when any of the following values are recorded ([Table 5](#)).

Table 5 Criteria for Administration of Eribulin Mesylate

a): Do not administer Cycle 1 Day 1 treatment where:	
Absolute Neutrophil Count	<1.0 × 10 ⁹ /L or 1,000/mm ³

Platelets	$<100 \times 10^9/L$ or 100,000/mm ³
Non-hematological toxicity	Any > Grade 2 except for inadequately treated nausea and/or vomiting
b): Do not administer any Day 8 treatment where:	
Absolute Neutrophil Count	$<0.75 \times 10^9/L$ or 750/mm ³
Platelets	$<75 \times 10^9/L$ or 75,000/mm ³
Non-hematological toxicity	Any > Grade 2 except for inadequately treated nausea and/or vomiting
c): Do not administer any subsequent Day 1 treatment where:	
Absolute Neutrophil Count	$<1.0 \times 10^9/L$ or 1,000/mm ³
Platelets	$<75 \times 10^9/L$ or 75,000/mm ³
Non-hematological toxicity	Any > Grade 2 except for inadequately treated nausea and/or vomiting

If the dose cannot be administered as planned due to treatment-related toxicity, the dose should be delayed according to the following instructions.

Day 1 of each cycle: If treatment cannot be administered on Day 1, the dosing should be delayed until recovery to above these values in [Table 5](#) or Grade ≤ 2 as appropriate (for Cycle 1 & subsequent cycles). The Day 1 dose will be rescheduled for when the criteria for treatment administration are met. The dose level may have to be reduced following a dose delay in accordance to the instructions for dose reduction ([Table 6](#) and [Table 7](#)).

Day 8 of each cycle: If treatment cannot be administered on Day 8, the dosing should be delayed until recovery to above these values ([Table 5](#)). The Day 8 dosing will be **delayed for a maximum of 7 days** and as follows:

- If recovery occurs on or before Day 15, dosing will be resumed at the next lower dose level ([Table 7](#)) and this will be the new Day 8.
- If hematological or non-hematological toxicity has not resolved to the above values on Day 15, the second administration in the cycle will be omitted. Dosing will be resumed at the next lower dose level ([Table 7](#)) and as scheduled on Day 1 of the next cycle if recovery has occurred to the above values.

Please note, use of hematopoietic growth factors is not permitted in Cycle 1 and is only permitted in subsequent cycles as per institutional guidelines.

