The treatment will be permanently reduced to the next lowest dose level ([Table 6](#)) after the occurrence of the following events:

Table 6 Criteria for Reduction of Eribulin Mesylate to the Next Lowest Dose Level

Absolute Neutrophil Count	Grade 4 neutropenia > 7 days Grade 3 or 4 febrile neutropenia and/or infection requiring treatment with antibiotics and/or growth factors
Platelets	Grade 4 thrombocytopenia Grade 3 thrombocytopenia requiring platelet or blood transfusion or both
Non-hematological toxicity	Grade 3 or 4 non-hematological toxicities (attributable to study drug); except Grade 3 hypophosphatemia, hypokalemia, hypocalcemia or hypomagnesemia that respond to supplementation

If hematological toxicities do not recover following a dose reduction to dose level -1 and the use of hematopoietic growth factors, the dose should be reduced to dose level -2. If non-hematological toxicities do not recover following a dose reduction to dose level -1, a second dose reduction to dose level -2 should be made. If either hematologic or non-hematologic toxicities do not recover despite two dose reductions, the subject should be discontinued from treatment. However, if the subject is deemed to have clinical benefit, continuation of treatment may be discussed with the sponsor.

Dose modifications are based on AEs for eribulin mesylate (starting dose determined by COG protocol ADVL1314/Eisai Study E7389-A001-113; 1.4 mg/m²; [Table 7](#)).

Dose level	Eribulin mesylate (mg/m²)
0*	1.4
-1	1.1
-2	0.8

* Dose level 0 refers to the starting dose.

Do not re-escalate dose level after the dose level has been reduced.

Instructions for QTc Prolongation on Electrocardiogram (ECG):

[figure not shown]
Increase the frequency of ECG and electrolyte monitoring in subjects who: develop Grade 2 QTc prolongation, are receiving agents that are known to prolong QTc interval, or have clinically relevant electrolyte abnormalities. Permanently discontinue eribulin mesylate in subjects who develop ≥Grade 3 QTc prolongation, and monitor ECGs and electrolytes frequently until the QTc interval returns to baseline.

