9.5.1.5 Pharmacokinetic, Pharmacodynamic, Pharmacogenomic, and Other Biomarker Assessments

9.5.1.5.1 PHARMACOKINETIC ASSESSMENTS

Samples for PK analysis of eribulin will be collected immediately post-infusion on Day 1 each cycle for 3 cycles, and pre-infusion and immediately post-infusion on Day 8 each cycle for 3 cycles (Table 9). Plasma concentrations of eribulin will be tabulated and summarized by dose level and time.

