7 CHANGES IN THE PLANNED ANALYSES

Not applicable.

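### The SAP summarises eribulin concentrations by histology where the protocol specifies dose level, so 7 of the 9 sampling points can mix dose levels, and no change is declared

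*SAP*

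**What the plan says.** Protocol 9.5.1.5.1 gives the rule for tabulating concentrations: "Plasma concentrations of eribulin will be tabulated and summarized by dose level and time". SAP 5.5.1 has the same sentence with a different grouping factor: "Plasma concentrations of eribulin will be tabulated and summarized by histology and time". The general layout rule in SAP section 5 does not bring dose level back: "All summary tables will be presented by histology type and overall". SAP section 7, which exists to record departures from the planned analyses, reads "Not applicable".

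The dosing rules in Protocol 9.4.1.1.1 start everyone at 1.4 mg/m² and allow reduction to 1.1 and then 0.8 mg/m². If a Day 8 dose is delayed and the subject recovers by Day 15, "dosing will be resumed at the next lower dose level", and that administration counts as the new Day 8. Reductions are permanent: "Do not re-escalate dose level after the dose level has been reduced".

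The protocol synopsis (Pharmacokinetic Analyses) also plans to overlay the observed concentrations on existing data and on "model-predicted 90% prediction intervals at the same dose level from other studies to demonstrate comparability in exposure". Neither SAP 5.5.1 nor SAP 5.5.2 mentions this overlay.

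**The concern.** Dose is the most obvious determinant of a plasma concentration, and it can change within subjects during the three sampled cycles. Once dose level is dropped as a grouping factor, a by-histology mean can fall from one cycle to the next, or differ between RMS, NRSTS and EWS, only because the mix of doses differs. The table as described would not reveal this.

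Evaluating exposure is a stated objective and the only exploratory endpoint. The synopsis overlay shows that the protocol treats dose level as the basis for comparing exposure. Because SAP section 7 records nothing, a reader cannot tell whether the switch was a decision or a drafting slip.

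**Working it through.** The documents give no figure to reproduce on this point. The check has two parts: a count of the affected time points, and an illustration of size.

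**Count.** SAP 5.5.1 schedules, in each of 3 cycles, one post-infusion sample on Day 1 and two samples (pre- and post-infusion) on Day 8. That gives 3 × (1 + 2) = 9 time points. A post-infusion sample reflects the dose just given. A Day 8 pre-infusion sample reflects that cycle's Day 1 dose. Each dose after Cycle 1 Day 1 may stay at the same level or drop one level, down to 0.8 mg/m², and may never rise.

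| Time point | Dose levels possible (mg/m²) |
|---|---|
| Cycle 1 Day 1 post | 1.4 |
| Cycle 1 Day 8 pre | 1.4 |
| Cycle 1 Day 8 post | 1.4, 1.1 |
| Cycles 2 and 3: Day 1 post, Day 8 pre, Day 8 post (6 points) | 1.4, 1.1, 0.8 |

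Points that can mix levels: 9 − 2 = 7. Grouped by dose level and time, as the protocol specifies, the number is 0.

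**Size.** The documents give no reduction rate for Cycles 1 to 3 and do not state that concentrations are dose-proportional, so both are assumed here. Under proportionality, the pooled mean relative to the 1.4 mg/m² mean equals the mean dose divided by 1.4.

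| Assumed mix at a time point | Mean dose (mg/m²) | Below the 1.4 mean |
|---|---|---|
| No reductions | 1.40 | 0% |
| 1 of 15 at 1.1 | (14 × 1.4 + 1 × 1.1)/15 = 1.38 | 1.4% |
| 3 of 15 at 1.1 | (12 × 1.4 + 3 × 1.1)/15 = 1.34 | 4.3% |
| 20% at 1.1, 5% at 0.8 | 0.75 × 1.4 + 0.20 × 1.1 + 0.05 × 0.8 = 1.31 | 6.4% |
| 40% at 1.1, 10% at 0.8 | 0.50 × 1.4 + 0.40 × 1.1 + 0.10 × 0.8 = 1.22 | 12.9% |

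**Contrast between histologies.** With 6 of 15 subjects at 1.1 mg/m² in one histology, the mean dose is (9 × 1.4 + 6 × 1.1)/15 = 1.28. With 1 of 15 in another it is 1.38. The apparent difference is 1 − 1.28/1.38 = 7.2%, with no difference in pharmacokinetics.

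**The case against.** The strongest reply is that this is one descriptive table for an exploratory endpoint in a single-arm study with a single starting dose. Protocol 9.7 leaves analysis detail to the SAP, and the protocol's own PK analysis section, 9.7.1.7.1, lists only sampling times. It is true that no decision depends on the table, and that limits the weight of the point. But 9.7.1.7.1 sets no competing grouping, so 9.5.1.5.1 is the protocol's only rule on tabulation. Replacing its factor is a change rather than added detail.

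Second, SAP 5.6.1 already summarises total dose, dose intensity and the number of subjects with dose changes, and SAP section 5 lays these out by histology. This would hint at an imbalance in dosing between histologies. It does not give the dose split at each PK time point, so the mixture could not be undone.

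Third, the percentages are hypothetical and start at 0%. That stands: 7 of 9 counts what is possible and is not an expected effect. The documents also give no between-subject variability to set the percentages against.

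Fourth, 0.8 mg/m² at Cycle 2 Day 1 needs two reductions after one cycle. The haematological route to that level refers to growth factor use, which the protocol does not permit in Cycle 1. The non-haematological criteria and the Table 6 events leave other routes. The count does not depend on this, since 1.4 and 1.1 mg/m² alone already make that time point mixed.

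Fifth, grouping by dose would not make the groups homogeneous. Six of the nine samples are taken immediately after infusion, and infusion may take 2 to 5 minutes or up to 15. That variation stays in any grouping and is no reason to add dose mix to it.

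Sixth, the overlay appears only in the synopsis, and SAP silence does not prove it was dropped. It is therefore a secondary item to reconcile, and the main point does not rely on it.

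**Conclusion.** The concern holds. The SAP's grouping contradicts the protocol's, the change is not declared, and 7 of 9 sampling points can pool dose levels: two levels at one point and up to three at six. The count follows from the documents alone. The size does not: the 0% to 12.9% shortfall and the 7.2% histology contrast rest on assumed dose proportionality and chosen reduction shares, and if nobody is reduced in Cycles 1 to 3 the effect is nil. The consequence is confined to an exploratory exposure summary and drives no study decision. The wording should still be corrected, because as written it confounds exposure with dose mix. The table shells are a separate document and were not available, so this applies to the SAP text.

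**What to change.** Amend SAP 5.5.1 so that concentrations are summarised by dose level and time. Define dose level as the dose most recently given before the sample, which for a Day 8 pre-infusion sample is that cycle's Day 1 dose. Present this for all histologies combined, and keep histology as an additional grouping so that the table still follows the layout rule in SAP section 5. Add the synopsis overlay on same-dose 90% prediction intervals to SAP 5.5.1. If the sponsor prefers to keep histology in place of dose level, or to omit the overlay, SAP section 7 should say so and give the reason.

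The cost is about two sentences and one revised table shell. No new data are needed, because the PK analysis set already requires "at least 1 evaluable plasma concentration and sufficient dosing information". The drawback is small cells at the reduced doses: at 5% of 45 subjects, about 2 would be at 0.8 mg/m². Showing all histologies combined eases this, and a small cell that is visible is preferable to one hidden in a pooled mean.
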